- a. There is minimal risk that the privacy of the patient's medical information could be breached.
- b. There is slight risk that participants could experience side effects from the intravaginal Phexxi, as listed in the drug information in Appendix F). However, as lactic acid is a substance that typically resides in the vagina, the likelihood of serious side effects from inserting it vaginally is low.

3. Protection against risk(s):

Please see Section III, #3 above regarding protection of patient's medical information. Regarding side effects of Phexxi, the patient will be adequately counseled on the side effect profile of the treatment, and instructed to discontinue the intervention if these side effects occur and are intolerable to the patient.

If participants develop side effects, the following will take place:

- The patient will be told to discontinue the study drug, and will be withdrawn from the study. This adverse event will be reported to the RIRC.

- If the patient marked on the ICF that they would like their primary Gyn provider to be notified in the case of an adverse event, the research team will send a secure chat message (through the EMR) the patient's primary provider.
- A follow-up visit will be scheduled with the patient to ensure that the unused study drug is returned to the research team
- The patient will be responsible for seeking care from their provider, and using their insurance plan to cover the costs of any treatment required.

4. Potential benefit(s) to the subject (direct medical benefit(s)):

The direct benefit to the subject includes potential prevention and resolution of their recurrent vulvovaginitis symptoms. Additionally, the Phexxi intravaginal gel is primarily used as a contraceptive agent, and thus if the treatment is used prior to intercourse, the patient will benefit from the contraceptive effects of the treatment.

5. Alternative to participation:

Declining participation will not affect patients' medical care, as patients will not be declined the standard of care treatment for BV or yeast infections, which are antibiotics or anti-fungal agents, respectively.

Section V: Subject Identification, and Consent/Assent

1. Method of subject identification and recruitment:

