Appendix B Patient demographic survey

Demographic Survey

Subject ID:

1: What is your age?:

2: What is your race?

3. Are you Hispanic/Latinx?

4.: How many yeast infections or episodes of bacterial vaginosis (BV) have you had in the last year?

5: Are you on any kind of birth control? If yes, what kind?

6: In the next portion, please describe what kinds of food you normally eat in a typical day. In addition to meals, please include snacks. If you are currently on a specific type of diet, please state that here.

Breakfast

Lunch

Dinner

Other

7 What other medical conditions have you been diagnosed with? If none, please write, "none".

8: Please list any medications/supplements you are currently taking. If none, please write, "none".

Appendix C. Survey to assess vulvovaginitis symptoms. Modified version of the Vulvovaginitis Symptom Questionnaire (VSQ)

During the past week, have you been bothered by:

1. Your vulva itching? 0 No 1 Yes

2. Your vulva burning or stinging? 0 No 1 Yes

3. Your vulva hurting? 0 No 1 Yes

4. Your vulva being irritated? 0 No 1 Yes

5. Your vulva being dry? 0 No 1 Yes

6. Discharge from your vulva or vagina? 0 No 1 Yes

7. Odor from your vulva or vagina? 0 No 1 Yes

8. Worry about your vulvar symptoms? (for example, that it will spread, get worse, scar, etc.) 0 No 1 Yes

9. The appearance of your vulva? 0 No 1 Yes

10. Frustration about your vulvar symptoms? 0 No 1 Yes

11. Embarrassment about your vulvar symptoms? 0 No 1 Yes

- 12. The effects of your vulvar symptoms on your interactions with others? 0 No 1 Yes
- 13. The effects of your vulvar symptoms on your desire to be with people? 0 No 1 Yes
- 14. Your vulvar symptoms making it hard to show affection? 0 No 1 Yes
- 15. The effects of your vulvar symptoms on your daily activities? 0 No 1 Yes
- 16. Your vulvar symptoms affecting your desire to be intimate? 0 No 1 Yes
- 17. Are you currently sexually active with a partner?
 No → Thank you. You are done with this questionnaire. Yes → Please proceed with the next 4 questions
- 18. The effects of your vulvar symptoms on your sexual relationships? 0 No 1 Yes
- 19. Your vulvar symptoms causing pain during sexual activity? 0 No 1 Yes
- 20. Your vulvar symptoms causing dryness during sexual activity? 0 No 1 Yes
- 21. Your vulvar symptoms causing bleeding during sexual activity? 0 No 1 Yes

Please use the space below to list any vulvar/vaginal symptoms you are experiencing which have not already been listed.

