Appendix F:

Table (taken from the Phexxi product information page) displaying the most reported adverse effects experienced after Phexxi use

Table 1. Adverse Reactions that Occurred in ≥ 2% of Subjects Who Used PHEXXI to Prevent Pregnancy (Studies 1 and 2 – U.S. population only)

Adverse Reaction	PHEXXI (N=2480) (%)
Vulvovaginal Burning Sensation	18.0
Vulvovaginal Pruritus	14.5
Vulvovaginal Mycotic Infection*	9.1
Urinary Tract Infection ^{†,‡}	9.0
Vulvovaginal Discomfort	9.0
Bacterial Vaginosis	8.4
Vaginal Discharge	5.5
Genital Discomfort	4.1
Dysuria	3.1
Vulvovaginal pain	2.1

* Includes preferred terms (PT) vulvovaginal mycotic infection and vulvovaginal candidiasis.
[†] Includes PTs urinary tract infection, streptococcal urinary tract infection, Escherichia urinary tract infection, and urinary tract infection bacterial.
[‡] Does not include PTs cystitis, kidney infection, and pyelonephritis [see *Warnings and Precautions (5.2)*].

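### Section IV.3 merges stopping the gel with leaving the study, so women who cannot tolerate it give no later swab or survey; acceptability (Survey C) is affected most clearly

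*Protocol*

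**What the plan says.** Section IV.3 (Protection against risk(s)) has two statements in sequence. The counselling sentence says that a woman is "instructed to discontinue the intervention if these side effects occur and are intolerable to the patient". The line that opens the bullets reads "If participants develop side effects, the following will take place" and states no severity. The first bullet is: "The patient will be told to discontinue the study drug, and will be withdrawn from the study". The adverse event goes to the RIRC, and the woman's own provider is told if she chose that. The only study contact described after withdrawal is this: "A follow-up visit will be scheduled with the patient to ensure that the unused study drug is returned to the research team".

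Section IV.2 ties the risk to "side effects from the intravaginal Phexxi, as listed in the drug information in Appendix F". That appendix is headed "Adverse Reactions that Occurred in ≥ 2% of Subjects Who Used PHEXXI to Prevent Pregnancy" and lists, among others, vulvovaginal burning (18.0%), pruritus (14.5%), discharge (5.5%) and pain (2.1%).

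Section III.1 places collection 2 at the end of the 30-day course and collection 3 thirty days after it. Survey B is given at baseline and at both later points. Survey C, the measure for the secondary outcome, is given only at the two later points. Under Section III.2 each woman is her own control; there is no comparison arm.

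**The concern.** Stopping a drug and leaving a study are separate events, and the first bullet makes one follow from the other. The women affected are those whose experience of the gel was worst. Their baseline data exist and the RIRC reports allow them to be counted, but their later symptoms, flora and opinion of the gel are not collected. A statistical analysis plan cannot recover data that the protocol never gathers. The 10% allowance in Section II.1 protects the number of completers, not the mix of women among them.

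Two results are exposed. Acceptability would be reported only by women who tolerated the gel. The symptom result rests on who supplies post-treatment answers, and the reason for leaving can be the same complaint that Survey B scores.

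**Working it through.** **1. What a withdrawn woman would still have supplied.** Side effects arise while the gel is in use, so a withdrawal for them normally falls before collection 2.

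| Measure | Planned times | Described after withdrawal? |
|---|---|---|
| Swab | baseline, 2, 3 | No |
| Survey B | baseline, 2, 3 | No |
| Survey C | 2, 3 | No, so she never rates the gel |

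The reminder for collection 3 is timed from completing the course, and the Appendix G email assumes that the course was completed. No route is written for a woman who stops early.

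**2. Threshold.** If the bullets cover only intolerable effects, fewer women leave; if they cover any side effect, more do. On both readings a woman with intolerable effects is withdrawn.

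**3. Overlap with Survey B (Appendix C).**

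| Appendix F | Survey B item |
|---|---|
| Pruritus | 1, itching |
| Burning | 2, "Your vulva burning or stinging" |
| Pain | 3, hurting |
| Discharge | 6, discharge |

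**4. How many leave.** The plan's own figure is 20 × 1.10 = 22 enrolled. Ten per cent of 22 is 2.2, so 2 leavers are used below. That treats the whole allowance, which also covers exclusions, as side-effect withdrawals. Four leavers are shown only to indicate scale.

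**5. Survey C.** Let *a* completers endorse an item, *b* leavers would have endorsed it, and *k* of *n* leave. Reported share = a/(n − k); share of all who started = (a + b)/n. The values of *a* and *b* are assumptions.

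- k = 2, a = 16, b = 0: 16/20 = 80% against 16/22 = 73%.
- k = 4, a = 14, b = 0: 14/18 = 78% against 14/22 = 64%.
- Leavers endorse at the completers' rate (k = 2, expected b = 2 × 0.8 = 1.6): 17.6/22 = 80%, no bias.

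**6. Survey B.** Assume no true effect and a normally distributed change, with positive meaning worse. Suppose the *k* women highest on some score leave, and that score has correlation ρ with the change. Completers then shift by −ρ × S/(n − k) SD of the change, where S is the expected sum of the *k* largest of *n* standard normal values. For n = 22 and k = 2, S = 1.91 + 1.46 = 3.37, and 3.37/20 = 0.168.

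*Leaving follows worsening:*

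| ρ (assumed) | 2 leave | 4 leave |
|---|---|---|
| 0 | 0 | 0 |
| 0.25 | −0.04 | −0.08 |
| 0.5 | −0.08 | −0.15 |
| 1 (upper bound) | −0.17 | −0.31 |

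*Leaving follows high baseline symptoms:* with pre-post correlation *r*, the baseline score has correlation −√((1 − r)/2) with the change. At an assumed r = 0.5 this is −0.5, so completers shift by +0.5 × 0.168 = +0.08 SD with 2 leaving (+0.15 with 4). That is against benefit: the most symptomatic women would on average have improved by regression to the mean, and their improvement is lost. At r = 0.3 or 0.7 the shift with 2 leaving is +0.10 or +0.07.

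**7. LAF/NLF.** Nothing in the protocol ties irritation from the gel to a change in flora, so no figure is given.

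**The case against.** Four arguments carry weight.

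- **The two thresholds need not conflict.** They are consecutive, and the bullets can be read as applying only to intolerable effects. The diary in Section III.1, which records side effects throughout the course, fits that reading. A reader might infer a contradiction; the text supports only an unclear threshold.
- **Direction for Survey B is not known.** A reader might infer that withdrawal tilts the symptom result towards benefit. Section II.2 lets symptomatic women enter, and if they tolerate the gel least the bias runs the other way by a similar amount. Survey B also asks "During the past week, have you been bothered by", so a woman who stopped in week 1 or 2 may have settled by collection 2.
- **Large false-positive figures are not supported.** With 2 leaving at correlation 1, a paired t-test would show a false benefit 15% of the time instead of 2.5%. That requires exactly the worst-changing women to leave. At correlation 0.5 it is 5.9%, and if the highest-baseline women leave (pre-post correlation 0.5) it falls to 1.1%. The protocol names a test only for LAF/NLF, an independent t-test, which is the outcome where the link is least supported.
- **This is an uncontrolled pilot of 22.** Even with full follow-up, an improvement could not be attributed to the gel. Asking a woman with irritation for two more swabs is also a burden.

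These arguments limit the claim about size and direction for Survey B. They do not touch the rule itself, which is explicit, or the selection in Survey C.

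**Conclusion.** The point stands as one to consider. Followed as written, Section IV.3 ends outcome collection for women who stop the gel because of side effects, whichever severity is meant.

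For Survey C the reported acceptability is probably too favourable. The illustration is 80% against 73%, and it rests on an assumed 16 of 20 endorsing and on neither leaver endorsing.

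For Survey B, loss can depend on the outcome. With 2 of 22 leaving and no true effect, the shift runs from about 0.04 to 0.08 SD of the change towards benefit (assumed correlation 0.25 to 0.5; upper bound 0.17) to about 0.08 SD against it (leaving by baseline symptoms, assumed pre-post correlation 0.5). The protocol does not say which applies. Appendix F rates come from contraceptive use, so they do not predict how many women would leave here.

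For LAF/NLF no direct link is shown. Appendix F does list bacterial vaginosis (8.4%) and mycotic infection (9.1%), and a reader might infer from this that flora-related loss is built in. The protocol does not say whether a recurrence counts as a side effect, so that inference is not supported.

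**What to change.** Replace the first bullet under Section IV.3 with:

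> Gel use stops if a side effect is intolerable or serious, or if a clinician advises it. Stopping the gel does not end study participation. Unless she withdraws consent, the woman is asked to complete Surveys B and C and, if she is comfortable doing so, the swabs, at the originally planned times of collections 2 and 3. The last dose date and any antibiotic or antifungal treatment with its dates are recorded.

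Keep RIRC reporting and the return of unused drug. Time the collection 3 reminder from the planned end of the course and adjust the Appendix G text. Include all women with post-baseline data in the pre-post analysis, and report how many stopped and why.

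As a sensitivity analysis, repeat the pre-post comparison without swabs taken during antibiotic or antifungal treatment or within 10 days after it, matching the baseline rule in Section III.1. A rule that counts treated women as not improved should not be added, because the protocol has no responder definition. The analysis details can sit in the statistical analysis plan; the collection rule has to be in the protocol.

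**Cost.** Protocol, consent and reminder wording must change. The take-home kit already holds the surveys and swab vials (Section III.1), and the second payment already depends on the third collection (Section V.8). Some samples will come from women off the gel or after treatment, which dilutes the result. The swab may be uncomfortable for women with irritation, so it is optional.

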Appendix A: Patient instructions for specimen collection

INSTRUCTIONS FOR SPECIMEN COLLECTION

1. Peel open the swab package. Remove the swab. Do not touch the soft tip or lay the swab down.
2. Hold the swab, placing your thumb and pointer in the middle of the swab shaft covering the score line. Do not hold the swab shaft below the score line. 3.
3. Carefully insert the swab into your vagina, about 2 inches (5 cm) past the vaginal opening, and gently rotate the swab for 10 to 30 seconds. Make sure the swab touches the walls of the vagina so that moisture is absorbed by the swab and then withdraw the swab without touching the skin.
4. While holding the swab in the same hand, unscrew the cap from the tube. Do not spill the contents of the tube. If the contents are spilled, contact the research team for a new collection tube.
5. Immediately place the swab into the transport tube so that the score line is at the top of the tube.
6. Carefully break the swab shaft at the score line against the side of the tube.
7. Immediately discard the top portion of the swab shaft.
8. Tightly screw the cap onto the tube.

Appendix B Patient demographic survey

Demographic Survey

Subject ID:

1: What is your age?:

2: What is your race?

3. Are you Hispanic/Latinx?

4.: How many yeast infections or episodes of bacterial vaginosis (BV) have you had in the last year?

5: Are you on any kind of birth control? If yes, what kind?

6: In the next portion, please describe what kinds of food you normally eat in a typical day. In addition to meals, please include snacks. If you are currently on a specific type of diet, please state that here.

Breakfast

Lunch

Dinner

Other

7 What other medical conditions have you been diagnosed with? If none, please write, "none".

8: Please list any medications/supplements you are currently taking. If none, please write, "none".

Appendix C. Survey to assess vulvovaginitis symptoms. Modified version of the Vulvovaginitis Symptom Questionnaire (VSQ)

During the past week, have you been bothered by:

1. Your vulva itching? 0 No 1 Yes

2. Your vulva burning or stinging? 0 No 1 Yes

3. Your vulva hurting? 0 No 1 Yes

4. Your vulva being irritated? 0 No 1 Yes

5. Your vulva being dry? 0 No 1 Yes

6. Discharge from your vulva or vagina? 0 No 1 Yes

7. Odor from your vulva or vagina? 0 No 1 Yes

8. Worry about your vulvar symptoms? (for example, that it will spread, get worse, scar, etc.) 0 No 1 Yes

9. The appearance of your vulva? 0 No 1 Yes

10. Frustration about your vulvar symptoms? 0 No 1 Yes

11. Embarrassment about your vulvar symptoms? 0 No 1 Yes

- 12. The effects of your vulvar symptoms on your interactions with others? 0 No 1 Yes
- 13. The effects of your vulvar symptoms on your desire to be with people? 0 No 1 Yes
- 14. Your vulvar symptoms making it hard to show affection? 0 No 1 Yes
- 15. The effects of your vulvar symptoms on your daily activities? 0 No 1 Yes
- 16. Your vulvar symptoms affecting your desire to be intimate? 0 No 1 Yes
- 17. Are you currently sexually active with a partner?
 No → Thank you. You are done with this questionnaire. Yes → Please proceed with the next 4 questions
- 18. The effects of your vulvar symptoms on your sexual relationships? 0 No 1 Yes
- 19. Your vulvar symptoms causing pain during sexual activity? 0 No 1 Yes
- 20. Your vulvar symptoms causing dryness during sexual activity? 0 No 1 Yes
- 21. Your vulvar symptoms causing bleeding during sexual activity? 0 No 1 Yes

Please use the space below to list any vulvar/vaginal symptoms you are experiencing which have not already been listed.

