The existing research on lactic acid-containing gel is promising. Of all studied methods of vaginal delivery of lactic-acid, including a douching system, a slow-release delivery pessary, lactic acid capsules, and a lactic acid-containing gel, the lactic acid-containing gel seems to be most effective. One study shows that the use of lactic acid gel as a treatment for bacterial vaginosis is comparable, but not superior to, the use of metronidazole^{8,9,10}. Currently, no research has been done on lactic acid gel as a prophylactic agent for patients who suffer from recurrent BV and/or yeast infections. This study aims to explore the feasibility and efficacy of a lactic acid-containing gel as prophylaxis against recurrent BV/yeast infections.

While several studies have been done which suggest that, as a treatment, intravaginal lactic acid gel is non-inferior to metronidazole, there have been no studies which explore its potential as a preventative agent. Compared to antibiotic therapies, lactic acid supplementation may be a more cost effective way to prevent BV and/or yeast infections, thereby reducing morbidities related to these conditions in patients who suffer from recurrent infections.

Section II: Criteria for Subject Selection

1. Number of subjects:

We will enroll a total of 22 patients. Using the Viechtbauer et al. method for calculating sample size in pilot studies¹¹, with a confidence level of 95% and probability of error prevalence estimated to at least 15%, the recommended sample size is 20. To account for exclusions and drop outs (estimated to be 10%), we should enroll a total of 22 patients.

2. Demographics of subjects:

Patients who undergo screening and are found to meet inclusion criteria will be invited to participate in this study.

Inclusion criteria

- Age 18-54
- Female
- Pre-menopausal
- Can speak and read in English
- Displays capacity for informed consent
- Has had 2 or more documented and/or self-reported episodes of symptomatic BV or candida infection in the last year, requiring, over-the-counter or prescription treatment

Exclusion criteria

- Pregnant or trying to become pregnant
- Post-menopausal
- Using NuvaRing device
- A past medical history of kidney disease, recurrent UTI, and/or urinary tract abnormalities
- Current UTI
- Using Phexxi as a contraceptive during the collection period of the study

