Once received at the research site, samples will be stored in a specimen freezer at -80 degrees F until all specimens are received, at which point they will analyzed using NextGen sequencing, a DNA sequencing technology that will identify the genetic makeup of their specimens. This will be done to sequence the genome of the bacteria of the microbiome, not the patient's genetic material. The first phase of the study will also include a survey (Appendix B), which will collect demographic information from each participant, as well as assess patients' current acceptability of a vaginal gel for prophylactic use, their most bothersome symptoms, and how their quality of life is affected by recurrent vulvovaginitis. The specific information collected from each

participant can be found below in Data Analysis. The survey used to measure this will be the **Vulvovaginal Symptom Questionnaire (VSQ)**, which has been validated for the purposes stated above (Appendix C). There will also be an added space in the survey provided for open-ended answers and comments.

Measurement for primary outcomes will be done using two separate methods. In order to assess for the presence of lactic acid-forming organisms before and after the lactic acid gel intervention, NextGen DNA sequencing will be completed on self-collected samples submitted by participants. The analysis of these samples will be performed by [name], at an in-house lab run by the UH Maternal Fetal Medicine division. In order to assess for patient-experienced symptoms, **survey B (Appendix C) will be administered prior to, immediately after, and 30 days after intervention.**

In order to measure our secondary outcome, Survey C (Appendix D) will be administered at collection points 2 and 3.

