Survey B, completed at the first, second and third collection time points will assess the symptom profile of each patient. Survey B is modified version of the VSQ (vulvovaginitis symptom questionnaire, which is a validated tool used to assess vulvovaginitis symptoms. A blank space will also be provided to allow for free text answers. These answers will be assessed qualitatively, looking for key themes within the answers provided.

To assess for the secondary outcome, Survey C, delivered at the second and third time point, will ask the patient what their satisfaction and acceptability ratings for Phexxi use as a prophylactic agent for vulvovaginitis are. Survey C is a validated tool, used to measure the acceptability, appropriateness, and feasibility of an intervention. A blank space will also be provided to allow for free text answers. These answers will be assessed qualitatively, looking for key themes within the answers provided.

3. Data storage, security, and confidentiality:

Patient information will be de-identified and connected to a unique Study ID. All identifiable information will be stored in a password protected and encrypted computer in the PI's research office at QMC, which is secured at the 1004 clinic. The signed consent forms will also be stored at the 1004 clinic, in a folder located in a locked office. Only the PI and [name] will have access to the identifiable information. [name], who will be performing analysis using specimens pre-labeled with the study ID, will not have access to participant PHI.

If participants opt, in their initial consent, to receive a copy of their vaginal microbiome results, the results will be sent to them via email, using a QMC email address. In order to encrypt this email, the function [encrypted] will be placed in the subject line.

4. Transition from research participation (if applicable): – Not applicable

5. Study timeline:

As the participation of subjects is not directly reliant on one another, data collection will begin as soon as the first subject is enrolled, and will continue until 30 days after the last subject completes the intervention. We hope for the total timeline to be approximately 1 year, which allow for time for data analysis and write-up of the intervention results.

Section IV: Risk/Benefit Assessment

1. Risk category (Minimal or Greater than Minimal): This study poses minimal risk to the patient.

2. Potential risk(s):

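### Survey B stops women who answer No at item 17 before they reach the free-text symptom box that the plan means to analyse for all participants

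*Protocol*

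**What the plan says.** Survey B is printed in Appendix C. Items 1-16 are yes/no symptom and impact items put to everyone. Item 17 asks about current sexual activity with a partner and splits the form. The No branch reads "Thank you. You are done with this questionnaire". The Yes branch reads "Please proceed with the next 4 questions", which leads to items 18-21. After item 21 comes the last element of the form: "Please use the space below to list any vulvar/vaginal symptoms you are experiencing which have not already been listed".

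Section III.2 sets the use of the form: "Survey B, completed at the first, second and third collection time points will assess the symptom profile of each patient". It then says of Survey B "A blank space will also be provided to allow for free text answers" and, on the analysis, "These answers will be assessed qualitatively, looking for key themes within the answers provided". Section III.1, describing the baseline survey and the VSQ, says "There will also be an added space in the survey provided for open-ended answers and comments". None of these statements restricts the free text to sexually active women.

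The inclusion criteria in Section II.2 rest on age, sex, menopausal status, language, capacity and infection history ("Has had 2 or more documented and/or self-reported episodes of symptomatic BV or candida infection in the last year"). Neither they nor the exclusion criteria mention sexual activity, so women who will answer No can enrol.

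**The concern.** The box asks about any unlisted vulvar or vaginal symptom. It has nothing to do with sexual activity, yet it sits behind a sexual-activity gate. A woman who follows the printed instruction never reaches it.

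The box has a real job to do, because the scored items have a gap. Items 1-5 (itching, burning or stinging, hurting, irritation, dryness) ask about the vulva only. Only items 6 and 7 (discharge, odor) name the vagina. The study product is an intravaginal gel, so vaginal itching or burning outside sexual activity has no scored item and would be reported in this box.

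What is at stake is the completeness of the qualitative symptom data. Text that was never invited cannot be recovered at the analysis stage, so a later analysis plan could not repair this.

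**Working it through.** **Step 1: routing in Appendix C.**

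| Answer at item 17 | Instruction | Items 18-21 | Free-text box |
|---|---|---|---|
| Yes | continue | reached | follows item 21, so reached |
| No | finished | skipped, as intended | no instruction leads to it |

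Skipping items 18-21 is sensible, since they concern sexual relationships and sexual activity. Skipping the box is a side effect of where it is printed.

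**Step 2: form against plan.** Section III.2 provides the space as part of Survey B, which is completed at three collections, and analyses the answers for themes. The form leads only the Yes branch to that space. The two do not match for any woman answering No. Item 17 is answered afresh each time, so the women affected can differ between collections.

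**Step 3: other places to write symptoms freely.**

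| Form | When | Could it replace the box? |
|---|---|---|
| Appendix B, demographic survey | baseline | No symptom question as printed; it asks for diagnoses, medications and diet |
| Appendix E, diary | the 30-day intervention | Partly: it has a column for side effects or symptoms and no sexual-activity gate |
| Appendix D, Survey C | collections 2 and 3 | Hardly: its comment space asks about experience with the product |

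At baseline nothing replaces the box. For the gel month the diary partly does. At collection 3 only the product comment remains.

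**Step 4: size.** The documents give no share of women answering No, so there is no stated figure to reproduce. For the number of women I take the protocol's own 20 evaluable out of 22 enrolled with 10% loss (22 × 0.90 = 19.8, about 20). The shares are assumptions.

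Women directed away at one time point = 20 × share answering No:
- 10%: 20 × 0.10 = 2
- 25%: 20 × 0.25 = 5
- 40%: 20 × 0.40 = 8

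Chance that at least one of 20 women is directed away = 1 − (1 − share)^20. At a share of 10% this is 1 − 0.9^20 = 0.88, and at 40% it is 1 − 0.6^20 > 0.999. With 22 women and 10% it is 1 − 0.9^22 = 0.90.

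The number whose text is actually lost is 20 × (share answering No) × (fraction of those with an unlisted symptom to report) × (fraction of those who obey the stop line). The last two fractions are unknown and at most 1, so 2, 5 and 8 are upper bounds.

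**The case against.** The strongest reply is that this is a layout slip of little consequence. Items 1-16, which include itching, burning, pain, irritation, dryness, discharge and odor, reach every woman. The box is optional and is printed on the form, so a woman may still fill it in. The diary collects free-text symptoms from all women during the gel month. All of this stands. It limits the point to the qualitative data and means that women are directed away from the box, not barred from it. It does not remove the mismatch between form and plan, or the gap at baseline.

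A reader might also infer more than the documents support:

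- *The missing text comes from the more affected women.* A woman may answer No simply because she has no partner. Items 16 and 18-19 ask whether symptoms affect intimacy; they do not presume it. Nothing shows that those answering No have worse symptoms.
- *An unlisted symptom could seem to appear or vanish after the gel.* A woman whose answer changes might supply text at some collections only, but Section III.2 plans themes within the answers given. It states no before-after comparison of free text.
- *Urinary symptoms go unrecorded.* Appendix F lists urinary tract infection (9.0%) and dysuria (3.1%) as adverse reactions, but the box asks for vulvar or vaginal symptoms, so moving it would not elicit urinary ones.
- *The same women are left out at all three collections.* Item 17 is answered anew each time. The third survey set goes out by an emailed link, and its online routing is not shown. If it follows the printed branch, the box might not appear at all after a No; that cannot be settled from the protocol.

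**Conclusion.** The point holds, with minor effect. As printed, Survey B directs women who answer No at item 17 away from a free-text box that the protocol plans and analyses without restriction by sexual activity. The consequence is confined to the qualitative symptom data. No scored item in 1-16 is affected, and neither selection bias nor a distorted before-after result is shown. The gap is clearest at baseline, where no other form offers free text on symptoms, and it carries some weight because items 1-5 cover the vulva only.

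The number of women affected is not known from the documents. The range of 2 to 8 directed away at a time point rests on assumed shares of 10% to 40% among 20 women and is an upper bound on the number whose text is lost. The conclusion itself rests on the printed item order and instructions, and on participants following them.

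**What to change.** In Appendix C, either move the free-text box above item 17, or reword the No branch so that it skips items 18-21 and continues to the box below. Use the same layout at all three collections and in any online version, and check the routing of the linked third survey set. Make the change before baseline forms are completed, since baseline text that was not collected then has no other source.

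The cost is one line on the form. It adds no item, visit or analysis, and the scored items stay as they are.
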